9.1. Site Selection

Sites participating in the PSR are located globally. At a minimum, the following criteria will be met before sites are selected for participation:

- Site clinicians are or will be users of Medtronic products
- Site has strong interest in active post-market surveillance

- Site has adequate resources, facilities, equipment and support staff
- Site can comply with registry requirements, local laws or regulations, and Medtronic requirements
- Sites are responsible for ensuring practicing clinicians are appropriately licensed/qualified
- Sites are responsible to ensure practicing clinicians are not debarred, disqualified, or working under sanctions in applicable regions
- PI qualifications confirmed

The role of the principal investigator (PI) is to implement and manage the day-to-day conduct of the registry as well as ensure data integrity and the rights, safety and well-being of the patients involved in the registry. The PI shall be qualified by education, training and experience to assume responsibility for the proper conduct of the clinical registry in accordance with the CIP and applicable local regulations.

9.2. Site Readiness

Prior to enrolling any patients into the PSR, sites must fulfill all local law, regulatory and sponsor requirements. The term Ethics Board will be used to define Institutional Review Board (IRB), Medical Ethics Committee (MEC), Research Ethics Board (REB), or Human Research Ethics committee (HREC). Participation readiness includes but is not limited to:

- Ethics Board approval or a written statement by the Ethics Board Chairperson or PI stating that approval is not required or documentation that approval is not required per local law
- Documented Ethics Board and sponsor approval of the ICF or DRF (if required), CIP and associated Addendums (as applicable)
- A legally executed Clinical Trial Agreement (CTA)
- Insurance certificates (as required per geography)
- Regulatory authority notification/approval, if required
- Documented training

Sites are authorized to enroll patients in accordance with the CIP. A list of sites, including PI and institutions, participating in the registry is available under a separate cover.

Medtronic will provide PSR participating sites with applicable registry materials (e.g., site binder). Note: If an AD (Refer to Section 6.2) is required, additional site readiness activities specific to the AD may be required.

9.3. Training

Training includes an overview of, but not limited to, registry objectives, purpose, consent process, design, data collection, reporting and applicable regulations.

Any registry personnel assisting with execution of PSR-related tasks will require CIP training on the activities pertinent to their involvement. Training will be documented. Additional meetings or conference calls may be scheduled to address ongoing site training. Following appropriate training, delegation of tasks will be documented.

10. Registry Procedures

10.1 Clinical Data Collection and Procedure Descriptions

Medtronic products may be used to monitor, diagnose and/or treat many medical conditions, therefore the following sections provide a general summary of the type of information gathered and procedures applicable for all PSR enrolled patients regardless of their condition, procedure, and therapy received (Refer to Table 1 for an example).

The PSR is an observational registry intended to collect data consistent with routine clinical care practices. Real-world clinical practice routines are not consistent across sites (i.e., physician preference, patient's condition and/or personal circumstances); therefore, to mitigate potential bias and ensure a robust data set, patient status is required to be reported at regular intervals regardless of whether the patients are seen in-person. Refer to the Condition/Therapy Appendix for more detailed data collection and procedure requirements for a particular patient condition and therapy.

Data collection is intended to reflect routine clinical care procedures and may include prospective and retrospective data. Data collection details and CRFs (where required) are provided under separate cover.

10.2 Schedule of Events

Table 1: Example of Data Collection Requirements

	Enrollment	Baseline	Procedure (*)	Follow-up	Exit
ICF or DRF Signed and Dated	X				
Demographics		X			
Outcome measures (if applicable)		X		X	X

	Enrollment	Baseline	Procedure (*)	Follow-up	Exit			
Medical History		X						
Device/System Information (if applicable)			X	X				
Procedure Details (*)			X					
Patient Status/Treatments		X	X	X	X			
System Modification/Retreatment			Upon Site's First Awareness					
Adverse Events	Upon Site's First Awareness							
Device Deficiencies	Upon Site's First Awareness							
Deaths	Upon Site's First Awareness							
CIP Deviations	Upon Site's First Awareness							

(*): Treatment initiation for those products which do not have a procedure

10.3 Informed Consent

Informed consent is defined as legally effective, documented confirmation of a patient's (or their LAR, legal representative, or guardian) voluntary agreement to participate in the PSR. Data Release Forms may also be utilized for the PSR since the PSR is focused on collecting real-world data available through medical records.

Patient consent will be obtained in accordance with local law and regulations. The ICF or DRF is signed only after all relevant information regarding participation has been provided to the patient. Consent must be obtained by PI or authorized designee. The ICF or DRF is applicable to all PSR patients as required. The ICF or DRF must include all information relevant to the patient's decision to participate. The ICF or DRF, and any applicable authorizations, must be approved by the sponsor and the site's Ethics Board unless an Ethics Board waiver for consent is obtained. The ICF or DRF documents must be maintained in such a way as to assure control of the document (i.e. version and/or date) such that the version(s) approved by the Ethics Board are clear with a documented change history for all revisions.

The process for obtaining informed consent shall:

- Avoid any coercion of, or undue/improper influence of patients to participate

- Not waive or appear to waive patient's legal rights
- Provide documents to the patient in a language she/he can read and understand
- Use language that is non-technical and understandable to the patient or legal representative
- Provide ample time for the patient to read and understand the ICF/DRF in order to consider participation
- Include a dated signature by the patient or legal representative acknowledging that their participation in the PSR is voluntary
- Include a dated signature by the responsible PI or authorized designee (if required by local law).

If the patient can't read or write, or is not able to fully understand all aspects of the registry, a witnessed and supervised (impartial third party) oral patient information consent is allowed as long as detailed documentation of the process is recorded in the patient's case history and the witness signs and dates the patient ICF or DRF on behalf of the patient. The ICF/DRF and any other information should be read aloud and explained within his/her ability to understand. Whenever possible, the patient/LAR shall sign ("make his mark", sign or otherwise physically mark the document to indicated consent) on the ICF/DRF. The impartial witness shall sign and personally date the ICF/DRF and Authorization (as determined by local law) to attest that the information was accurately explained, and consent was freely given.

Vulnerable patients are individuals who are unable to fully understand all aspects of the registry that are relevant to the decision to participate, or who could be manipulated or unduly influenced as a result of a compromised position, expectation of benefits or fear of retaliatory response. Examples of vulnerable patients may include a(n) infant, child and juvenile, seriously ill or unconscious patients, or patients with a mental or intellectual disability. Special consideration is required for vulnerable patients when considered for PSR participation. Patients who are considered "vulnerable" are to be consented according to the relevant local laws and regulations of the country in which they are located, as well as any other institutional requirements that apply, including those specified by the Ethics Board.

Unless waived by the Ethics Board, the signed ICF or DRF and the authorization (as determined by local law) must be filed at the site. A signed and dated copy of the ICF or DRF and any other authorizations, must be provided to the patient. The original signed ICF or DRF and the authorization (if required) or other privacy language where required by law, must be retained and made available for review by sponsor site monitors, auditors, or regulatory inspectors.

The consent process should be documented at each site, at minimum, with a progress note in the patient's case history. The consent process should ensure important new information is provided to patients throughout the registry, which may relate to the patient's willingness to continue participation in the registry. The consent process should follow local laws and regulations as applicable.

The ICF and DRF templates are not updated with each CIP revision unless the revision impacts the elements of the ICF or DRF template. The ICF and DRF can be revised independently of the CIP.

Medtronic must approve any adaptation of the templates. For all sites requiring an ICF or DRF, the Ethics Board, Medtronic and regulatory authorities, if applicable, must approve the final ICF or DRF.

10.4 Baseline

The enrollment and baseline visit can occur at the same time. A general summary of the type of patient information collected at baseline includes but is not limited to:

- Confirmation of eligibility
- Demographics
- Medical history
- Baseline outcome measures for specific therapies and/or patients

10.5 Procedures

A general summary of the type of information collected at procedure or start of treatment includes but is not limited to:

- Device information (e.g., model, serial number)
- General relevant procedure information (e.g., placement methods & location, technique, and device measurements, as applicable by therapy)

10.6 Follow-up

Patient follow-up collection requirements are intended to generally align with the routine clinical care practices of the patient care providers consistent with real-world data collection. Refer to the applicable Condition/Therapy Appendix for follow-up frequency and data submission requirements specific to a given patient condition, procedure and/or therapy.

10.6.1 Frequency of Follow-up

At least one status update is to be reported annually for all PSR enrolled patients or until follow-up is complete, patient exit or death, or surveillance of the product is no longer active.

Refer to the applicable Condition/Therapy Appendix for the follow-up/data submission requirements for a given patient condition, procedure and/or therapy, which may be more frequent than annually.

The minimum follow up/data submission frequency is intended to facilitate regular updates regarding patient/device status and assess site reporting compliance.

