10.12 Subject Exit, Withdrawal or Discontinuation

The rationale for patient exit should be documented in the patient's case history. Patients may be exited from the PSR under the following circumstances:

- Patient chooses to withdraw (e.g., consent withdrawal)
- PI deems withdrawal necessary (e.g., medically justified, failure of patient to maintain adequate registry compliance)
- Patient enrolled (signed ICF or DRF) prior to procedure or anticipated product use but procedure and/or product used not eligible for PSR enrollment
- All enrolled eligible products are inactive (e.g., electrical abandonment, product explant)
- Patient death
- Patient is no longer available for follow-up (i.e., lost to follow-up, refer to 10.6.4)

NOTE: If the patient is determined to be lost to follow up, documentation will be obtained, and the patient may be exited from the PSR. In addition, requirements set-forth by the Ethics Board must be followed by sites.

- Site closure
- Patient has completed PSR follow-up requirements

11. Risks and Benefits

There are no expected additional benefits or risks relative to participation in the PSR as data is being collected on routine medical care and all products are market-released. Products eligible for enrollment are market-released and should be used in accordance with approved labeling.

12. Adverse Events and Device Deficiencies

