- Surgical History
- Vital signs
- Quality of Life or satisfaction measurements, if applicable

B.3 Procedure

The following types of data may be collected for enrolled patients as applicable for the procedure performed:

- Perioperative details
- Device details
- Adverse Events, Device Deficiencies, Deaths, and deviations are to be reported to Medtronic upon awareness
- Imaging, if applicable
- Procedure recordings, if applicable
- Quality of Life or satisfaction measurements, if applicable

[figure not shown]
[figure not shown]
B.4 Follow-up Reporting Frequency & Data Collection

Patients will be treated in accordance with the routine clinical practices of their respective care provider. However, in 'real world' clinical practice, the frequency of in-person follow-up visits may vary for many reasons (e.g., patient's personal circumstances, condition, physician preference, etc.) resulting in more or fewer in-person visits.

As a result, the PSR is based on an active surveillance model which requires sites to complete a patient status assessment post-procedure, regardless of whether the patient is seen in-person per the physician's routine follow-up care practices. This approach ensures a robust dataset while increasing the continual awareness of patient status throughout their registry participation.

Data will be captured through 30 days post-procedure (to be reported between day 30 and 37) at a minimum and may be captured up to 60 months (or 5 years) post-procedure (Figure 1).

For procedures requiring long-term follow-up data, assessments will be collected at least annually with a maximum follow-up duration of 60 months at which time the patient will be exited (Figure 1). The total duration of follow-up for products requiring long-term follow-up data collection will be determined by various factors including but not limited to product lifecycle, recurrence rate, or regulatory requirements. The timing of the patient assessments and exit will be outlined in the corresponding Analysis Plan or Addendum. Refer to Figure 2 for an example of a long-term follow-up data collection schedule.

Surgical Appendix - Figure 1: Follow-up Schedules**Surgical Appendix - Figure 2: Example of a Long-term Schedule**

Follow-up data will be collected for enrolled patients and may include, but are not limited to:

- Patient status
- Readmissions
- Imaging information, if applicable
- Procedure recordings, if applicable

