Surgical Appendix - Table 3: Definitions for Event Severity

Event type	Severity Definition
Mild event	Signs, or symptoms that are easily tolerated by the subject, or are clinical or diagnostic observations of the investigator.
Moderate event	Signs, or symptoms that cause discomfort and interfere with normal functioning. Local or non-invasive intervention may be indicated.
Severe event	Signs, or symptoms that disable the subject, are medically significant, lead to hospitalization or prolongation of hospitalization.

B.6 Lost to Follow-up

Follow-up data may be collected via medical record review within the expected reporting period. In cases where a subject interaction is required for a study endpoint, subjects may be considered lost to follow-up if at least two attempts to contact the subject are unsuccessful. The method of attempt (e.g., one letter and one phone record, or two letters) must be documented in the subject's source documentation. In addition, regulation set forth by the governing EC/IRB must be followed.

B.7 Exit

Enrolled patients will be exited from the registry once the applicable duration of follow-up has been completed unless exited early for unavoidable reasons. Patients with an ongoing reportable Adverse Event or Device Deficiency at the time of final registry timepoint will be followed until resolution for up to 30 days after the final registry timepoint, or other applicable period as defined in the analysis plan or addendum.

B.8 Schedule of Data Collection

Surgical Appendix - Table 4: Data Collection Schedule

	Enrollment and Baseline	Procedure	Follow-up Assessment
Informed Consent, if applicable	X		
Patient status		X	X
Demographics and Medical and Surgical History	X		
Vital signs	X	X	X
Procedure information		X	
Imaging, if applicable	X	X	X
Product and/or therapy information, if applicable	X	X	X
Quality of Life or satisfaction measurements, if applicable	X	X	X
Readmission			X
Reintervention		Reported upon site awareness	
Procedure/Device Related Adverse Events		Reported upon site awareness	
Device Deficiencies		Reported upon site awareness	
Deaths		Reported upon site awareness	
Deviations	Reported upon site awareness		

C. Data Collection Details

Data collection details and CRFs (where required) are provided under separate cover.

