#### 7.9.1.3 Analysis Method

Event rate is calculated as number of events divided by number of units (e.g. subjects or product uses) where events are evaluated among subjects who have enrolled, met all the inclusion/exclusion criteria, and underwent surgical procedure. If there are more than one event per unit, only the first event is relevant to the primary objective.

Two-sided 95% confidence interval (CI) of the event rate will be calculated using Binomial distribution. All the events will be summarized in a table by Medical Dictionary for Regulatory Affairs (MedDRA)

terms. The number of events, and the number and percentage of subjects who experienced the event will be reported. Surgical or medical procedure related events and/or the product related events will be listed.

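### The protocol lets status updates stop when product surveillance ends, with no matching exit reason, and the SAP's long-term primary rate counts every patient with short follow-up as event-free

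*Protocol*

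**What the plan says.** Protocol 10.6.1 sets a minimum of one status update a year, "until follow-up is complete, patient exit or death, or surveillance of the product is no longer active". The end of product surveillance is listed there as a stop of its own, apart from completed follow-up, exit and death.

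Protocol 10.12 introduces its exit reasons with "Patients may be exited from the PSR under the following circumstances" and gives eight. None names the end of product surveillance. The two nearest are "Patient has completed PSR follow-up requirements" and "All enrolled eligible products are inactive (e.g., electrical abandonment, product explant". Protocol 16.10 describes termination for a site or for the whole registry, not for a product.

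Surgical Appendix B.7 states: "Enrolled patients will be exited from the registry once the applicable duration of follow-up has been completed unless exited early for unavoidable reasons". It does not define those reasons. Appendix B.4 caps follow-up at 60 months and says that the total duration for long-term products "will be determined by various factors including but not limited to product lifecycle, recurrence rate, or regulatory requirements". It adds: "The timing of the patient assessments and exit will be outlined in the corresponding Analysis Plan or Addendum".

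On analysis, SAP 4.1 allows a primary time point as late as 5 years. SAP 7.9.1.3 defines the estimator: "Event rate is calculated as number of events divided by number of units (e.g. subjects or product uses". The denominator is every enrolled, eligible subject who had the procedure, only the first event per unit counts, and the interval is binomial. SAP 7.4 uses observed data and leaves any imputation to a study-specific addendum. Kaplan-Meier appears only in 7.9.2, for secondary survival outcomes. SAP 3 commits any report that contains one of these objectives to the method written here.

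**The concern.** There are two linked gaps. The first is in the record. A site that stops updating a patient because surveillance of the product has ended has no exit reason to enter, and no stated rule for the date to which the patient's status is known. A later analyst may be unable to tell that patient from one who was fully observed.

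The second is in the estimator. A proportion over all treated units answers a 5-year question correctly only if each patient is either observed to 5 years or has the event before follow-up stops. Otherwise unobserved time is read as event-free time. The error goes one way, towards a lower event rate, and it enters the primary result of a registry meant to detect emerging safety and performance problems.

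**Working it through.** **Passages compared.** Protocol 10.6.1 has four stops: follow-up complete, exit, death, and surveillance no longer active. The first three each have a place in 10.12; the fourth has none. Of the two nearest reasons, the one on inactive products is illustrated by events to the patient's own device, so it does not describe surveillance ending. The one on completed requirements could cover the case if ending surveillance shortens what is required, but 10.6.1 lists completion separately. Appendix B.7 neither admits nor excludes the stop.

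**Plan's own figure.** SAP 6.1 uses N = 1.96² × p(1 − p) / halfwidth². For p = 10% and halfwidth 5%: 3.8416 × 0.09 / 0.0025 = 138.3, rounded up to 139, as tabulated. All nine cells of the table reproduce. The formula has no input for incomplete follow-up.

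**Size of the bias (illustration).**

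- From SAP 6.1: true rates P of 10%, 15% and 20%, with N = 139, 196 and 246 at halfwidth 5%. From SAP 4.1: a 5-year time point.
- Assumed, because the documents give nothing: a share f of patients stops at year t; the hazard is constant; stopping is unrelated to risk.
- Hazard: λ = −ln(1 − P)/5. For P = 10%, λ = 0.10536/5 = 0.02107 per year.
- Event probability by year 2: 1 − exp(−2 × 0.02107) = 4.13%.
- Expected crude rate: (1 − f) × P + f × (1 − exp(−λt)).
- f = 10%, t = 2: 0.9 × 10% + 0.1 × 4.13% = 9.4%.
- f = 30%, t = 2: 0.7 × 10% + 0.3 × 4.13% = 8.2%.
- f = 50%, t = 2: 0.5 × 10% + 0.5 × 4.13% = 7.1%.

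The same formula for P = 10% at other stopping times:

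| Stop at | f = 10% | f = 30% | f = 50% |
|---|---|---|---|
| Year 1 | 9.2% | 7.6% | 6.0% |
| Year 2 | 9.4% | 8.2% | 7.1% |
| Year 3 | 9.6% | 8.8% | 8.1% |

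**Effect on the interval.** This is the coverage of the true 5-year rate by an exact (Clopper-Pearson) 95% interval, stopping at year 2:

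| N, P | None stopped | 10% stopped | 30% stopped |
|---|---|---|---|
| 139, 10% | 96.8% | 96.9% | 94.3% |
| 196, 15% | 96.4% | 95.2% | 85.0% |
| 246, 20% | 96.2% | 94.4% | 76.4% |

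With few patients stopped, the interval still does its job. With 30% stopped, it depends on the cohort: little is lost at N = 139, and a good deal at N = 246.

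**The case against.** The best reply is that the base documents leave room to settle all this elsewhere. Appendix B.4 ties duration to product lifecycle and sends exit timing to the Analysis Plan or Addendum. SAP 7.1.3 allows analysis sets to be limited by time frame or cutoff, and SAP 7.4 allows an addendum on missing data. Those documents were not available for this review. This stands as a limit on the finding, but no text in the base documents requires an addendum to deal with short follow-up, and SAP 3 makes the crude rate the default.

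A reader might infer several stronger things that the documents do not support:

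- *That B.7 forbids the stop.* Its early-exit wording is open, and 60 months is a maximum, not a promised duration.
- *That these patients leave with no exit form or date, by sponsor decision.* The protocol does not say that they skip exit, and 10.6.1 does not say who ends surveillance. What is missing is a named reason and a date rule.
- *That late events go unreported.* Reporting on first awareness is a separate duty and continues while the patient participates. Detection may weaken, but the duty remains.
- *That the 10.6.1 clause causes the bias.* The estimator causes it. A patient who withdraws, is lost to follow-up or is at a closed site, with a complete exit record, is counted in the same way.
- *That the bias is typically large, or tied to poorly performing products.* Spreading everyone's follow-up evenly over 2 to 5 years would turn 10% into 7.1%, but that cuts short essentially every patient. No text links the end of surveillance to performance.

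The constant hazard is also open to challenge. The endpoint includes procedure-related events, and several listed in Appendix Table 2, such as bleeding and wound dehiscence, would be expected early. An early peak in hazard would shrink the bias.

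**Conclusion.** The concern holds in two limited parts. Protocol 10.6.1, 10.12 and Appendix B.7 are not aligned on the end of product surveillance and need reconciling. Separately, for long-term time points, the SAP 7.9.1.3 rate is biased low by any follow-up that ends early in a living patient without an event. Ended surveillance is one route to this among several.

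The direction is firm: with all treated units in the denominator, unobserved time can only lose events. The size is not known. The figures of 9.4% and 8.2% against a true 10% rest on an assumed stopped share, a constant hazard and stopping unrelated to risk. Thirty-day rates are little affected. Secondary Kaplan-Meier outcomes can censor these patients, although the SAP does not state the censoring date.

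**What to change.** 1. **Protocol 10.12:** add an exit reason for ended product surveillance, with an Exit CRF and the date of last confirmed status. Have Appendix B.7 say whether this is an allowed early exit.
2. **SAP 7.9.1.3:** for long-term time points, estimate the event rate from time to first event, censored at last confirmed status, as 1 minus Kaplan-Meier with the log-log interval already specified in 7.9.2. The SAP already counts only the first event per unit, so no new event definition is needed. State how death without an event is handled, since it is not ordinary loss of follow-up.
3. **Reporting:** keep the crude proportion as a supplementary figure and give the number of subjects with incomplete follow-up.

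The 10.6.1 clause need not be deleted. It is Core text for all therapies, and how long to keep updating patients is a resourcing choice for the sponsor.

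The cost is one exit code, a few sentences, slightly more analysis work and a slightly wider interval. Under Protocol 16.6 a protocol revision needs Ethics Board and sponsor approval, so the change in step 1 is best carried in the next planned revision. The new estimator removes the bias only if stopping is unrelated to event risk, which the recorded exit reasons would help to judge.
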